Potential mechanisms by which EEN might act include relative bowel rest, reduced antigenic load, provision of trophic amino acids, local anti-inflammatory effects, and modification of gut microbiota^{11,20}. However, there is no strong evidence to fully support any one of these mechanisms. A recent meta-analysis²⁰ showed that the effects of the therapeutic formula on specific bacterial strains were variable and inconsistent among studies, possibly due to small sample sizes and methodological limitations. Our preliminary data showed that short term dietary changes improve motility in patients with low-grade gut inflammation²¹. However, the effects of EEN on gastrointestinal transit in adults has not been yet investigated.

Evidence for the effect of EEN on quality of life, an essential patient reported outcome, is particularly scarce. Guo *et al*³⁰ found an improvement of quality of life in 13 patients with CD receiving EEN for 6 weeks. However, it is currently unknown whether EEN is more effective than CS in improving quality of life in adults with CD.

The potentially synergistic effects of adding EEN to CS therapy have not been explored before. Therefore, we designed a randomized controlled trial with the objective to investigate the effect of EEN in addition to different regimes of CS therapy (ECS) compared to CS alone (CS), for decreasing disease activity and improving quality of life in adult patients with CD. We also propose to investigate potential mechanisms underlying any beneficial effect of EEN in CD in the context of concomitant CS therapy.

Hypotheses:

- 1- Six weeks of ECS will be more effective than CS in inducing clinical remission in patients with active CD
- 2- Six weeks of EEN in addition to a short course of CS (ECSC) will have similar efficacy than ECS and reduced number of adverse events
- 3- Six weeks of ECS will lead to beneficial changes in the composition and/or metabolic activity of the intestinal microbiota, gastrointestinal transit and inflammatory burden.

Because the effect size of ECS has not been investigated before, we will perform a pilot study to assess feasibility and calculate estimates of effect size in order to plan a larger trial. Based on the significant number of patients, if the study is feasible, we will consider the sample size estimated through this pilot study for the full trial to minimize the possibility of recruiting additional patients.

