General aim and endpoint: To assess study feasibility and provide estimated effect sizes (point estimates with confidence intervals) for all measures of interest in order to plan an adequately powered study. We will assess recruitment rates and acceptability of treatment in arms involving exclusive enteral nutrition.

Primary outcome and endpoint: To assess the efficacy of 6 weeks of ECS in inducing remission (CDAI <150) compared to treatment with CS in adult patients with active CD (CDAI >220 and either CRP >5 or fecal calprotectin >250 mg/l).

Secondary outcomes and endpoints: To determine the beneficial effect of 6 weeks of ECS as compared to CS in inducing:

1. Clinical disease improvement (drop in CDAI >70 or 100)
2. Improvement in quality of life (using the Inflammatory Bowel Disease Questionnaire (increase IBDQ scores))
3. Biochemical remission (normalization of either serum CRP and/or fecal calprotectin)
4. Changes in microbiota composition (16S sequencing Illumina)
5. Normalization of colonic transit (SHAPE 0-5 markers at day 5)³⁴ among those with altered transit at baseline
6. Decrease in anxiety and/or depression scores (decrease >2 points HAD-A and/or HAD-D scores)
7. Increase in body weight and improvement in nutritional status (increased levels of micronutrients)
8. Decrease of indirect markers of mucosal integrity (IFABP2)
9. Changes in bacterial fermentation profile (SCFAs: acetate (acetic acid), propionate (propionic acid), and butyrate (butyric acid))^{26,27}.
10. Decreased number of adverse events

METHODS

Study design

Protocol date: October 2018

Randomized control trial; 3 arms of treatment: EEN plus standard or short course of CS (ECS, ECSC) vs CS alone (CS) conducted at McMaster University Medical Centre (Figure 1). The study will last 10 weeks and will involve 4 visits. At the screening visit, we will assess clinical history and symptoms, perform a physical exam and complete bloodwork after the informed consent is signed. Randomization will occur at the second visit (pre-treatment), when the inclusion and exclusion criteria and symptoms will be re-assessed, and baseline stool and urine samples will be collected. In addition, we will perform a SHAPE study and patients will be assessed by a dietitian or clinical nutrition support specialist to assess dietary factors and estimate energy needs using the Harris Benedict equation as detailed below.

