Patients will be instructed to take the allocated treatment and to collect empty bottles/blisters of medication to assess the compliance at the next visit. Six weeks later (visit 3), their symptoms will be re-assessed, blood, urine and stool samples collected and SHAPE study performed. Patients will be instructed to stop the EEN or decrease the dose of CS, as detailed in the section “Follow up after treatment”. In the last visit (4th visit; 10 weeks after enrollment) we will collect information on symptoms, stool samples and urine.

The study protocol will be submitted by the investigator for approval by the Hamilton Integrated Research Ethics Board (HiREB).

Randomization process

The sequence of the treatments will be randomly generated using a computer-based pseudo-random number generator (RStudio Team (2015). RStudio: Integrated Development for R. RStudio, Inc., Boston, MA) Patients will receive one of challenges A,

B, or C consisting of CS, ECS or ECSC. A third person not involved in the study will perform the randomization to preserve treatment allocation concealed from participants and study staff. A block randomization will stratify patients by disease location (colonic/small bowel involvement). Each treatment will be assigned a number according to the randomization sequence. On recruitment, the patient will be assigned into one of three strata and given the next consecutive randomization number available for that stratum. Treatment will be not blinded for patients or study staff.

Subject recruitment

Subjects will be recruited from McMaster University Medical Centre (MUMC) Digestive Diseases Clinic, identified in an ongoing database organized in 2008 and by recruitment flyers posted at McMaster University Medical Centre, Juravinski Hospital and Hamilton General Hospital. Patients in the database signed an informed consent agreeing to be contacted for future research. Patients will be contacted by study personnel and invited to participate in the study.

After the subject has provided written consent to participate, an inclusion checklist will be completed. Subjects will be enrolled after having fulfilled all inclusion criteria, and none of the exclusion criteria.

Participants

One hundred adult patients diagnosed with IBD will be recruited at McMaster University Medical Centre. This will provide 30 subjects in each treatment arm, allowing for 10% dropout rate.

Inclusion criteria:

1. Adult patients (age 18-75 years)

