Patients randomized to ECS or ECSC arms will receive EEN defined as enteral feeds given exclusively as sole nutritional source over 6 weeks period in addition to the CS therapy. Hypercaloric polymeric formula (Modulen 1.5 kcal /ml; Nestle ^{22,23}) will be used for a period of 6 weeks. To increase palatability, patients will be allowed to add the “Nestle Nutrition Flavour Mix” (see Appendix). Daily volumes of formula will be prescribed based upon the patient’s estimated energy requirement (EER), calculated using the Harris Benedict equation (calculator available at <https://manytools.org/handy/bmr-calculator>), which estimates basal metabolic rate from weight and height and then applies an activity factor which ranges from 1.2 to 2.4 (Sedentary AF 1.2; mild activity 1.375, moderate activity AF 1.55, heavy activity AF 1.7, extreme AF 1.9 For details, refer to Appendix). Actual body weight or ideal body weight for height will be used in the equation depending on whether the patient is of an appropriate weight or underweight for height. Oral administration will be encouraged wherever possible, with formula volume distributed as set meals and snacks throughout the day. Nasogastric (NG) tube insertion for delivery of formula will be discussed and offered only if oral supplementation is not possible or not tolerated by the patient. Enteral feeding will be prescribed as an exclusive therapy, with exclusion of all normal diet for the period of feeding. Patients will be reviewed after 3 weeks of therapy and, when required, energy intakes will be modified by adjusting formula volumes based upon adequacy of weight changes. Volume taken per meal and distribution during the day will be recorded in the case report form. No oral foods or fluids

(except for clear liquids including water and weak tea or coffee) will be allowed during the study period. Vitamins and supplements will be allowed if doses have been stable before entering in the study, and doses are not changed during the study.

2. Corticosteroids

Patients in ECS and CS arms will receive oral prednisone 40 mg x day for 2 weeks; with subsequent taper of daily dose by 5 mg per week. Patients randomized to ECSC arm will receive oral prednisone 40 mg x day for 3 days and taper in 16 days (Figure 1). Patients randomized to the CS arm will be asked to maintain their regular diet.

Follow up after treatment

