Appendix 2-Steroids adverse events assessment (visit 2)

	Yes/no	Comments
1. Moon face		
2. Bloating		
3. Swelling		
4. Weight gain		
5. Increase appetite		
6. Hair loss		
7. Acne		
8. Stretch marks		
9. Insomnia, restlessness and or trouble sleeping		
10. Anxiety or nervousness		
11. Depression		
12. Anger/irritability		
13. Generalized weakness or fatigue		
14. Joint pain		
15. Hot flushes		
16. Visual problems (light sensitivity, decreased visual acuity)		
17. Nausea, vomiting		
18. Diarrhea		
19. Dizziness		
20. Headaches		
21. Hypertension		
22. High glucose levels		

Nestlé Nutrition Flavour Mix

Description

Nestlé Nutrition Flavour Mix is a flavouring powder formulated for use with Peptamen® Vanilla Cup and Modulen® IBD.

Presentation

60g tub (with a 0.6g scoop). Available in 5 flavours: Banana, Lemon & Lime, Chocolate, Strawberry and Coffee.

Indications

ACBS approved, prescribable on FP10 (GP10 in Scotland). For use with Vanilla flavoured Peptamen® and Modulen® IBD.

Ingredients

Banana Flavour

Dextrose, Flavouring (contains Maltodextrin), Maltodextrin, Anti-caking agent (Silicon dioxide), Colour (Curcumin), Sweetener (Sucralose).

Coffee Flavour

Dextrose, Soluble Coffee solids, Anti-caking agent (Silicon dioxide), Colour (Caramel E150c), Sweetener (Sucralose).

Strawberry Flavour

Dextrose, Flavouring (contains Maltodextrin), Acidity regulators (Lactic acid, Acetic acid), Stabiliser (Gum arabic), Preservative (Sulphur dioxide), Anti-caking agent (Silicon dioxide), Colour (Beetroot red), Sweetener (Sucralose).

Lemon & Lime Flavour

Dextrose, Flavouring (contains Maltodextrin), Modified starch, Antioxidant (E320), Citric acid, Anti-caking agent (Silicon dioxide), Colour (Curcumin), Sweetener (Sucralose).

Chocolate Flavour

Dextrose, Flavouring (contains Maltodextrin), Stabilisers (Glycerine, Gum arabic), Molasses, Anti-caking agent (Silicon dioxide), Colour (Caramel E150c), Sweetener (Sucralose).

All Flavours: Milk, Egg, Soya, Nut, Gluten and Lactose free.

Administration and dosage

Suggested intake: Add 2 scoops Nestlé Nutrition Flavour Mix per 100ml.

Shelf life and storage

Shelf life of 12 months from date of manufacture when stored at room temperature.

Contraindications

Not for intravenous use.

Not suitable for children under 3 year of age.

Precautions

To be used with caution in children between 3 and 5 years of age.

Suitable for use in children over 5 years of age.

Must be used under medical supervision.

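### Planned safety observation stops almost as soon as the standard prednisone course ends, and the steroid adverse-event checklist is assigned to a pre-treatment visit

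*Combined protocol and SAP*

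**What the plan says.** On length and visits, the Study design section states: "The study will last 10 weeks and will involve 4 visits". Visit 2 comes before treatment: "Randomization will occur at the second visit (pre-treatment), when the inclusion and exclusion criteria and symptoms will be re-assessed". Visit 3 is six weeks later. Visit 4 is described as follows: "In the last visit (4th visit; 10 weeks after enrollment) we will collect information on symptoms, stool samples and urine". Adverse events are not in that list.

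On prednisone, the Corticosteroids section says "Patients in ECS and CS arms will receive oral prednisone 40 mg x day for 2 weeks", followed by weekly steps of 5 mg. The standard-course table in Figure 1 carries the same steps and adds a tenth week at 5 mg on alternate days. The short-course table reaches 5 mg on alternate days at day 16 and then zero.

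On harms, Hypothesis 2 expects that ECSC "will have similar efficacy than ECS and reduced number of adverse events". The secondary outcomes open with "To determine the beneficial effect of 6 weeks of ECS as compared to CS in inducing", and item 10 is "Decreased number of adverse events". The section on handling adverse events covers everything that occurs during the study, with no stated start or end. A sentence that safety follow-up continues appears under Early withdrawals and gives no duration or schedule. The steroid checklist has 22 items and is headed "Appendix 2-Steroids adverse events assessment (visit 2)".

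**The concern.** Two features of the schedule limit what the trial can learn about steroid harms.

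First, the study closes at about the time that CS and ECS patients take their last tablet. Any event that appears when prednisone is stopped, or shortly after, falls largely outside planned observation in the two arms with the larger exposure. It falls well inside it in ECSC.

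Second, the one structured tool for steroid effects is tied to a visit at which no study prednisone has been taken. Followed literally, it yields a baseline with nothing to compare it against.

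At stake is the completeness of the safety data, in a pilot that is meant to supply estimates for a larger trial. An undefined adverse-event window could be carried into that trial.

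**Working it through.** **Inputs.** First dose is day 1. Visit 4 at 10 weeks is day 70 or 71 if enrollment is the day of first dose (assumption). The standard-course table is labelled for ECS; the Corticosteroids text gives CS and ECS the same course.

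**Last dose.**
- Standard course, table: week 10 is days 64 to 70 on alternate days, so the last dose is day 69 or 70.
- Standard course, text: 14 days at 40 mg, then seven weekly steps from 35 to 5 mg. 14 + 7 × 7 = day 63.
- ECSC: day 16 if the final entry is a single dose, or day 22 if alternate-day dosing runs for a week (assumption). The text, read as 3 + 16 = 19 days, lies inside this range.

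**Days observed after the last dose = day of visit 4 − day of last dose.**

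| Arm and schedule | Lowest | Highest |
|---|---|---|
| CS, ECS (table) | 70 − 70 = 0 | 71 − 69 = 2 |
| CS, ECS (text) | 70 − 63 = 7 | 71 − 63 = 8 |
| ECSC | 70 − 22 = 48 | 71 − 16 = 55 |

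**Sensitivity to the start date (assumption).** If first dose came 4 to 5 days after enrollment, for example to allow for the baseline day-five x-ray, visit 4 would fall on day 65 to 67. On the table that is 2 to 5 days before the last dose (67 − 69 = −2; 65 − 70 = −5). On the text it is 2 to 4 days after. ECSC would have 43 to 51 days. Nothing in the protocol says that treatment waits for the x-ray, so the conclusion does not rest on this case.

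**Exposure.**
- Standard course, text: 40 × 14 + 7 × (35 + 30 + 25 + 20 + 15 + 10 + 5) = 560 + 980 = 1540 mg.
- Standard course, table: add 3 or 4 doses of 5 mg, giving 1555 to 1560 mg.
- ECSC: 3 × (40 + 30 + 20 + 10 + 5) = 315 mg, plus 1 to 4 doses of 5 mg, giving 320 to 335 mg.
- Ratio: 1540/335 = 4.6 to 1560/320 = 4.9. This measures exposure, not risk after stopping.

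**Is the comparison biased?** Observed time per arm of 30 is 30 × 70 = 2100 to 30 × 71 = 2130 person-days, the same in every arm. Each extra off-prednisone day in ECSC is matched by an observed on-prednisone day in ECS. That difference is part of the randomised strategy, so a 10-week count compares the strategies fairly over 10 weeks.

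**If adverse events are compared at week 6.** Visit 3 is day 42 or 43. CS and ECS patients are then finishing 20 mg/day, with 7 × (15 + 10 + 5) = 210 mg (text) or 225 to 230 mg (table) still to take. ECSC has been off prednisone for 42 − 22 = 20 to 43 − 16 = 27 days.

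**The case against.** The best defence is that little is lost. All adverse events during the study are recorded, serious or not and related or not. Visit 4 collects symptoms, and further findings on an event can go to a follow-up file. The taper is gradual, and the study covers all or nearly all of it. Most checklist items, such as moon face, appetite, acne and insomnia, read as on-treatment effects. The protocol names no harm expected after stopping and gives no rate for one. Item 10 sits under a six-week heading and contrasts ECS with CS, two arms on the same prednisone schedule. The visit 2 label may be a numbering slip, and a figure not reproduced in the text may hold a fuller visit schedule.

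Most of this stands, and it limits the size of the point. It does not close the gap. The general recording clause has no window, the follow-up sentence concerns patients who leave treatment early, and unprompted reporting does not replace a structured checklist repeated on treatment.

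Two stronger readings are tempting. A reader might infer that the ECSC-versus-ECS adverse-event comparison is biased because ECSC is watched for weeks off prednisone. The documents do not support that: calendar time is equal, no direction can be derived, and no text makes the 10-week count the analysis. A reader might also infer that on-treatment steroid harms go unrecorded. The general adverse-event section contradicts that; only the structured checklist is affected.

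**Conclusion.** The point holds as a minor safety improvement. CS and ECS have about 0 to 8 days of planned observation after stopping prednisone, depending on whether the table or the text governs; ECSC has about 7 weeks. The steroid checklist, as labelled, is a pre-treatment baseline with no later visit named for it in the available text. The day counts assume that first dose falls on the day of enrollment and that the short course ends between day 16 and day 22. The primary outcome, the ECS-versus-CS contrast and the validity of a 10-week adverse-event count are not affected. If adverse events are meant to be compared at week 6, only the safety follow-up is affected.

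**What to change.** 1. Keep the Appendix 2 checklist at visit 2 as the baseline and repeat it at visits 3 and 4 in all arms. This uses visits that already exist.
2. State whether the table or the text sets the last standard-course dose.
3. Add one brief safety phone contact in every arm at a common time, about two weeks after the last scheduled standard-course dose: about day 85 from first dose.
4. Define one adverse-event window for all arms, from first dose to that contact, compare arms over it, and say whether a week-6 count is also reported.

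Doses, tapers, clinic visits and sampling times stay as they are. The cost is about two more weeks of follow-up and about 100 short calls, one per recruited patient.

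The limits should be stated in the plan. A call cannot measure blood pressure or glucose, which are 2 of the 22 checklist items. Off-prednisone time also remains longer in ECSC: 85 − 22 = 63 to 85 − 16 = 69 days, against 85 − 70 = 15 to 85 − 69 = 16 (table) or 85 − 63 = 22 (text). Harms that appear later than that after stopping would still be seen in ECSC only.

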2. Confirmed CD diagnosis for at least 6 months
3. Clinically active disease (CDAI >220 or HBI>6) or evidence of activity in endoscopy
4. Biochemical evidence of disease activity (CRP > 5 and/or fecal calprotectin > 250),

Exclusion criteria:

1. Current treatment with EEN
2. Intestinal obstruction, perforation, toxic megacolon, massive gastrointestinal bleeding, abdominal abscess, or other criteria considered by the investigator which preclude the use of EEN;
3. Stricture disease
4. Previous intestinal resection with a remnant bowel <180 cm
5. Treatment with prednisone in last 30 days;
6. New start or change in dose of azathioprine, 6-mercaptopurine, cyclosporine, other immunosuppressant or biologics in the last 90 days. Doses of these medications must also remain unchanged for the duration of the study.
7. New start or change in dose of 5ASA in last 30 days. 5ASA dose must remain unchanged for the duration of the study.
8. Treatment with antibiotics or probiotics use in the last 30 days.
9. Pregnancy or lactation
10. Any serious illness considered by the investigator that will interfere with the study procedure or results.

Intervention

Participants will be randomized to one of the following interventions:

1. Exclusive enteral nutrition plus corticosteroids

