Following the completion of the period of exclusive enteral feeding, patients receiving EEN will be instructed to gradually reintroduce foods by adding one individual item every 2 days as shown in Table 1 ^{32,33} and Appendix with instructions for food introduction with coincident reduction of formula volumes under the supervision of an expert in Nutrition. The accelerated introduction of foods was based on a recent study showing similar results with additional benefits of 2 days vs 4 days ³³.

Treatment compliance

The subjects will be asked to keep the cans of Modulen and blister packs of prednisone during the entire treatment period and bring them back to the investigator at the end of that period. Compliance will be recorded in the CRF. In order to improve assessment of patient's compliance, 2 copies of a paper sheet diary will be provided at Visit 1. Patients

consuming <80% of the prescribed treatment dose throughout the study, or those who interrupted therapy for more than three consecutive days will be considered as noncompliant.

Measurements before and after treatment

- Clinical data regarding demographics, disease location and activity (Harvey-Bradshaw Index), social life and habits, past and current clinical medical background, previous surgeries, nutritional status (malnourishment, weight/ height) will be collected in CRF.
- Dietitian/ Certified nutrition support clinician: Dietary habits and caloric intake will be recorded at baseline with nutritional assessment during visits
- Bloodwork to assess for inflammatory markers, CRP, fecal calprotectin, ESR, as well as CBC, platelets, micronutrients (albumin, vitamin D, B12, A, zinc, copper, chromium)
- Questionnaires: McMaster Food frequency questionnaire(Hamilton, ON), quality of life (SIBDQOL¹³), disease activity (CDAI), anxiety and depression (HAD score, Beck inventory), and nutritional assessment (Subjective Global Assessment¹⁴ Braun Nutriscreen program)
- Gastrointestinal transit (colonic transit: SHAPE study and orocecal transit^{24,25}: patient will take one capsule and have an x ray on day five, following R.C. Evans, et al protocol, where ≥ 6 markers indicate delayed transit, therefore ≤ 5 is normalization of colonic transit).³⁴
- Stool sample (frozen samples) for microbiota composition (16S sequencing Illumina; Dr. [name]'s lab) metabolomics and metagenomics ([name]?)¹⁵

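### The trial is open-label and its primary endpoint is CDAI <150 alone; the week-6 markers that could test that result are not tied to it, and masked reading is not planned

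*Combined protocol and SAP*

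**What the plan says.** The Randomization process section states "Treatment will be not blinded for patients or study staff". The same section says "A third person not involved in the study will perform the randomization to preserve treatment allocation concealed from participants and study staff". That sentence concerns concealment of the sequence before assignment; it does not mask anything afterwards. No masked outcome assessor, film reader, laboratory or analyst is described anywhere. Under Intervention, the CS arm keeps its usual diet, so each patient knows whether the formula was added.

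The primary outcome is "To assess the efficacy of 6 weeks of ECS in inducing remission (CDAI <150) compared to treatment with CS". Under Measurements before and after treatment, the Questionnaires item includes "disease activity (CDAI), anxiety and depression (HAD score, Beck inventory").

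Inclusion criterion 4 requires "Biochemical evidence of disease activity (CRP > 5 and/or fecal calprotectin > 250"). At outcome the same markers form secondary endpoint 3, "Biochemical remission (normalization of either serum CRP and/or fecal calprotectin"). Study design has blood and stool collected at visit 3, the primary time point. The Statistical analysis section plans no analysis that relates CDAI remission to either marker.

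Colonic transit is a count on a day-5 film: 6 or more "markers indicate delayed transit", and 5 or fewer is normal.

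The Hypotheses section says that the pilot is to yield effect-size estimates for planning a larger trial, and that the sample size estimated from it will be considered for that trial.

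**The concern.** Patients and staff know who received the added treatment, and the primary result depends on whether a questionnaire-based score falls below a fixed cut. A difference between arms in how symptoms are reported or scored would be counted as a difference in remission. More patients would not remove it, because it is bias and not noise, and it would pass into the planning of the full trial.

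The protocol already collects measurements that a reporting shift does not directly move. As written they are a weak check. The biochemical endpoint can be read as needing either marker or both, it does not say what happens to a marker that was normal at entry, and its result is not tied to the reading of the primary one. The transit endpoint turns on a single-marker difference in a film count, and nothing provides for that count to be made without knowledge of arm.

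**Working it through.** **The plan's own figure.** Three arms of 30 with 10% dropout: 90 / (1 − 0.10) = 100, which matches the stated total. No alpha, power, remission rate for CS or ECS, or CDAI SD is given. What follows is therefore illustration under assumed values.

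**Shift entering the primary endpoint.** Assume normally distributed week-6 CDAI, true remission of 60% in both arms, and reported CDAI lowered by a mean of *d* points in ECS only. Then

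false difference = Φ(0.253 + *d*/SD) − 0.60, with Φ(0.253) = 0.60.

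| *d* | SD 70 | SD 80 | SD 100 |
|---|---|---|---|
| 10 | 5.4 | 4.7 | 3.8 |
| 20 | 10.5 | 9.3 | 7.5 |
| 30 | 15.2 | 13.5 | 11.0 |

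Entries are percentage points. A shift against ECS would lower the difference instead.

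**Carry-over to the full trial.** Assume true rates of 60% and 75%, a two-sided 5% level, 80% power, and

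n = [1.960·√(2p̄(1 − p̄)) + 0.842·√(p₁(1 − p₁) + p₂(1 − p₂))]² / (p₂ − p₁)².

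- Unbiased, 60% against 75%: n = 151.9, so 152 per arm.
- A 20-point shift at SD 80 moves 75% to Φ(0.674 + 0.25) = 82.2%. This is a 7.2-point gain, smaller than the 9.3 points at 60% because fewer patients lie just above the cut. 60% against 82.2% gives about 64 per arm.
- With 64 per arm, power for the true 60% against 75% is about 44%.

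**Would a composite of CDAI <150 and a normal marker be an independent check?** Take the 20-point case with no true effect: CDAI remission is 60.0% in CS and 69.3% in ECS, so 9.3 points are false. If a share *s* of the falsely added remitters also meet the marker rule, the composite moves by 9.3 × *s*:

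- *s* = 20%: 1.9 points
- *s* = 40%: 3.7 points
- *s* = 60%: 5.6 points
- *s* = 80%: 7.4 points

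The composite moves in favour of ECS for any *s* above zero, because it contains the open-label CDAI. Its agreement in direction with the primary endpoint is therefore expected under pure reporting bias. In this scenario the marker difference by arm, taken over all patients, does not move.

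**Precision.** With 30 per arm, the 95% half-width for 60% against 75% is 1.96·√(0.24/30 + 0.1875/30) = 23.4 points. For a marker-remission rate *p* common to both arms it is 1.96·√(2*p*(1 − *p*)/30), which is 23.2 to 25.3 points for *p* between 40% and 70%.

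**The case against.** Exclusive formula against ordinary food can hardly be masked, this is a feasibility pilot, and the first hypothesis concerns clinical remission, which CDAI <150 measures. Inflammation is covered by the third hypothesis and by secondary endpoint 3. All of that stands: it is a reason to keep the primary endpoint and not to ask for a masked diet.

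Sampling error in the pilot is also larger than every illustrated shift (23.4 points against at most 15.2). That limits what any one result can show. It does not cancel a bias, which shifts the centre of the interval.

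Several stronger readings are tempting, and the documents do not support them:

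- A reader might infer that the bias favours EEN. Both arms receive prednisone, and EEN patients give up normal food for six weeks and may be offered a nasogastric tube. That burden could worsen reported well-being, so the direction is open.
- A reader might infer that film readers and laboratory staff know the arm. The protocol does not say who counts markers or runs assays; it says only that study staff are not blinded and provides for no coding.
- A reader might infer that the trial cannot separate reported from inflammation-free remission. CDAI, CRP and calprotectin are planned for the same patients, so a cross-tabulation remains possible. What is absent is its pre-specification.
- The CDAI components are not listed, so how much of the score is self-reported cannot be shown from the documents.

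**Conclusion.** The point holds in a limited form. An open-label trial with CDAI <150 as its sole primary criterion leaves the ECS-CS remission difference exposed to a reporting or scoring shift in either direction. The marker data that could inform its reading are collected but loosely defined and unlinked to it. Bias is possible, not shown.

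Its size rests wholly on assumed SD, shift and remission rates: at SD 80 and 60% remission, 4.7 to 13.5 points for shifts of 10 to 30 CDAI points. The sample-size figures rest on the same kind of assumption and show only the mechanism.

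A reader might infer that a CDAI-plus-marker composite pointing the same way as the primary result would confirm it. It would not, since reporting bias alone moves both together. The useful comparison is the marker difference itself. At 30 per arm that difference is imprecise, so it informs interpretation and cannot settle the question.

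**What to change.** 1. **Keep CDAI <150 as primary and fix the marker rule.** Define biochemical remission at week 6 as every marker that was raised at entry being no longer above its entry cut (CRP no longer >5, calprotectin no longer >250). Inclusion criterion 4 ensures that each eligible patient has at least one such marker. Report the ECS-CS difference with its confidence interval beside the primary result, and pre-specify a CDAI-by-marker cross-tabulation by arm. State that a CDAI benefit will be described as supported by objective evidence only in light of the marker difference itself, not because a composite containing CDAI agrees in direction. Fix this before outcome data are seen.
2. **Limit the open-label statement to patients and treating staff.** Label x-ray films, blood and stool with code numbers so that marker counts (the 5 against 6 cut) and assays are read without knowledge of arm. This protects those secondary endpoints; it does not mask CDAI scoring.
3. **Optionally, keep the arms coded for the analyst** through derivation of the intention-to-treat endpoints. The Randomization process section already uses labels A, B and C. Coding cannot extend to the per-protocol set, because excluding patients non-compliant with enteral nutrition would reveal the EEN arms.

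Cost: protocol wording, a little extra labelling and one additional table. No new visits, samples or staff are needed, and the total stays at 100. The stricter marker rule will give fewer biochemical successes than the either-marker reading.
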